STOP CRC Program (NIH R01) Statistical Analysis Plan

Official Trial Title: Culturally Adapted Multilevel Decision Support Navigation Trial To Reduce Colorectal Cancer Disparity Among At-Risk Asian American Primary Care Patients

Unique Protocol ID: R01MD012778

Document Date: 3/1/2018

Lead Organization: University of Maryland

Participating Site Information: University of Maryland School of Public Health

NCT Number: NCT03481296

CONTACT INFORMATION:

[name], Principal Investigator
[name]
Department of Epidemiology and Biostatistics
University of Maryland School of Public Health
[name] 20742-2611
[contact]
[contact]

[name], MS, Central Contact
[name]
Department of Epidemiology and Biostatistics
University of Maryland School of Public Health
[name]
[contact]
[contact]

Statistical Analysis Plan

Determine overall screening adherence in the culturally adapted decision support navigation intervention vs. the advanced control. The two study groups will be compared in terms of the fraction of participants who undergo colorectal cancer screening (through stool blood test or colonoscopy) within 12 months of the randomization date. Screening status will be determined using the 6-month survey, 12-month self-report of screening, and medical record review data at 6 and 12 months. We hypothesize that participants in the culturally adapted decision support navigation intervention group will have higher overall colorectal cancer screening rate than participants in the advanced control group. Generalized Estimating Equation (GEE) models with a logit link will be used to adjust for nesting of participants within primary care physicians. Specifically, the dependent variable is the screening status (yes vs. no) and the main predictor is the intervention groups (culturally adapted decision support navigation intervention versus advanced control). As mentioned above, we expect the two study groups to be comparable at baseline due to randomization. So, the model will control only for participant gender, age, and ethnicity (Chinese or Korean) (these three variables will be included to allow addition of interaction between study group and gender, age, or ethnicity in secondary analyses). If, however, substantial baseline imbalances occur, the model will control for additional variables.

Measure change in colorectal cancer screening decision stage in the culturally adapted decision support navigation intervention vs. the advanced control. We will elicit colorectal cancer screening decision stage separately for stool blood test and colonoscopy (decided against, not considering, undecided, decided to do), and compute an overall colorectal cancer screening decision stage as the higher of the two test-specific decision stages. We will elicit decision stage both at the baseline survey and at the 6-month survey. Forward change (between baseline and 6-month) will encompass any movement from a lower to a higher decision stage. We hypothesize that participants in the culturally adapted decision support navigation intervention group will have a greater likelihood of forward movement in screening decision stage than participants in the advanced group. We will analyze forward change in screening decision stage (yes vs. no (no change or backward movement between baseline and 6 months)) via a logit link to control for participants nested within primary care physicians. The model will adjust for participant baseline characteristics if necessary.

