- (1) Implement a randomized controlled trial among 400 Chinese and Korean American primary care patients to compare colorectal cancer screening outcomes between the culturally-adjusted decision support navigation intervention and advanced control;
- (2) Determine overall colorectal cancer screening adherence and change in colorectal cancer screening decision stage in the culturally adapted decision support navigation intervention versus advanced control; and
- (3) Evaluate intervention reach, effectiveness, adoption, implementation, and maintenance.

Study Design

This study employed a cluster randomized control trial intervention study design. Participants were assigned to either the advanced control group or culturally adapted decision support navigation intervention group

Study Population

Enrollment

Twenty Chinese and Korean primary care physicians will participate in the study. Twenty Chinese and Korean American participants will be recruited from each participating primary care physicians' clinics in Maryland and Northern Virginia (in total, 400 Chinese and Korean American patients will participate in the study).

Inclusion Criteria

Eligible participants met the following inclusion criteria: male and female Chinese and Korean American patients aged 50 to 75, who are not up to date for colorectal cancer screening.

Exclusion Criteria

Those with a family history, previous history of removing polyps, inflammatory bowel disease, or diagnosis of colorectal cancer.

Procedures

- (1) Ten primary care physician clinics will be randomized to advanced control and other 10 primary care physician clinics will be randomized to the culturally adapted decision support navigation intervention. Accordingly, 200 Chinese and Korean Americans (20 participants from 10 primary care physician clinics) will be randomized to the advanced control and other 200 Chinese and Korean Americans (20 participants from 10 primary care physician clinics) will be randomized to the culturally adapted decision support navigation intervention. In total, 400 Chinese and Korean Americans will participate in this project.

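### With only 20 randomised clinics and no small-sample correction specified, the usual GEE sandwich z test would have a type I error of about 7.5–9.5%, not 5%

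*SAP*

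**What the plan says.** **Design.** Under Enrollment, the Protocol says "Twenty Chinese and Korean primary care physicians will participate in the study", and that 20 patients come from each clinic. Procedures, item (1), gives the allocation: "Ten primary care physician clinics will be randomized to advanced control and other 10 primary care physician clinics will be randomized to the culturally adapted" intervention. That is 10 clinics against 10, and 200 patients against 200.

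**Main analysis.** In its paragraph on overall screening adherence, the SAP says: "Generalized Estimating Equation (GEE) models with a logit link will be used to adjust for nesting of participants within primary care physicians". The outcome is binary (screened or not within 12 months), and "the model will control only for participant gender, age, and ethnicity (Chinese or Korean"), with more variables added if baseline imbalance is substantial.

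**Decision-stage analysis.** Forward movement in decision stage is to be analysed "via a logit link to control for participants nested within primary care physicians". A link function does not itself account for nesting. A GEE was very probably meant.

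**What is absent.** Neither document gives a working correlation, variance estimator, reference distribution, degrees of freedom, small-sample correction, alpha or sidedness.

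**The concern.** The robust (sandwich) variance of a GEE is justified as the number of clusters grows, not the number of patients. With 10 clinics per arm, the uncorrected version is biased downward, and the normal quantile ignores the uncertainty in a variance estimated from about 18 degrees of freedom. Both faults make p-values too small and intervals too narrow.

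This test decides whether the navigation intervention is said to raise screening. The candidate methods differ by about 3–4 points in type I error and 6–12 points in power, so the choice could change the conclusion. It should be made before the data are seen.

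The size of the problem depends partly on whether ethnicity varies within clinic. A covariate that is constant within clinic uses up a further between-clinic degree of freedom. The Enrollment text ("Twenty Chinese and Korean American participants will be recruited from each participating primary care physicians' clinics in Maryland and Northern Virginia") can be read as mixed clinics but does not settle the matter, so both cases are worked.

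**Working it through.** **Inputs from the documents.** 20 clinics, 10 per arm, 20 patients per clinic (Protocol, Enrollment and Procedures item 1). Binary outcome, logit-link GEE, covariates gender, age and ethnicity (SAP). The only design figure to reproduce is the sample size: 20 × 20 = 2 × 10 × 20 = 400, which agrees. No alpha, power, effect size or ICC is given.

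**Assumptions.** Two-sided 5%. For the simulations, a screening rate of 30% or 50% and an ICC of 0.02, 0.05 or 0.10.

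**1. Approximation without simulation (unadjusted, m = 10 equal clinics per arm).** The uncorrected sandwich variance is (m − 1)/m = 9/10 of the unbiased between-clinic variance. Hence:

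- Uncorrected variance, z test: 2·P(t₁₈ > 1.96·√0.9) = 2·P(t₁₈ > 1.859) = 7.9%.
- Uncorrected variance, t₁₈ critical value: 2·P(t₁₈ > 2.101·√0.9) = 2·P(t₁₈ > 1.993) = 6.2%. Changing the reference distribution alone is not enough.
- Valid width over uncorrected width: 2.101 / (1.96·√0.9) = 1.13.

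No ICC or screening rate enters. If ethnicity acts as one more clinic-level parameter, a rough version replaces 9/10 by 17/20 and 18 df by 17: 2·P(t₁₇ > 1.96·√0.85) = 2·P(t₁₇ > 1.807) = 8.8%.

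**2. Simulation of the adjusted model under the null.** Exchangeable GEE, beta-binomial clinics, 20 × 20, arms allocated 10:10, adjusted for gender, age and ethnicity. There were 10,000 trials in each of 12 scenarios (Monte Carlo standard error about 0.3 points). The GEE code agreed with statsmodels on the estimate, robust SE and bias-reduced SE.

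| | Ethnicity mixed within clinic | Ethnicity constant within clinic |
|---|---|---|
| Uncorrected sandwich + z | 7.7–8.2% | 8.7–9.5% |
| Uncorrected sandwich + t | 5.9–6.3% | 6.7–7.5% |
| Kauermann-Carroll + t | 4.7–5.1% (18 df) | 4.7–5.3% (17 df) |
| Mean SE / true SD, uncorrected | 0.92–0.94 | 0.89–0.91 |
| Coverage of nominal 95% CI, uncorrected z | 91.8–92.4% | 90.5–91.3% |
| CI width, Kauermann-Carroll + t over uncorrected z | 1.13 | 1.18 |

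Mancl-DeRouen with z gave 4.5–5.4% over the same scenarios.

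**3. Variations (screening rate 30%, 8,000 trials each).** Uncorrected sandwich with z:

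- Arm-only model: 7.4–7.8%.
- Clinics split 90/10 by ethnicity: 8.4–8.6%.
- Unequal clinic sizes (CV about 0.5, assumed): 8.4–9.4% mixed, 10.4–11.5% constant. In this setting Kauermann-Carroll + t gave 5.4–6.3% and Mancl-DeRouen + z gave 5.1–5.7%.

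**4. Replication with separately written code.** Rates of 20, 40 and 60%, ICC 0.01, 0.05 and 0.10, about 4,000 trials per scenario (Monte Carlo standard error about 0.4 points). Uncorrected sandwich with z, mean and scenario range:

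- Unadjusted: 8.0% (7.1–8.7%).
- Adjusted, clinic-level ethnicity balanced by arm: 8.6% (8.0–9.2%).
- Adjusted, clinic-level ethnicity not balanced by arm: 9.3% (8.2–9.8%).
- As the last, with clinic sizes of 10–30: 9.9% (8.7–10.9%).

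Kauermann-Carroll + t gave means of 4.8–5.5% across these settings. Further simulation runs gave 7.1–8.6% (mixed) and 8.8–10.7% (constant) for the uncorrected z test with equal clinics.

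**5. Power (5,000 trials per scenario).** For 30% versus 45% at ICC 0.05 (assumed), moving from uncorrected z to Kauermann-Carroll + t takes power from 63.7% to 54.1% (mixed) or from 66.2% to 54.3% (constant). Across eight scenarios the loss was 6.3–12.4 points.

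**The case against.** The strongest reply is that the SAP never says an uncorrected variance will be used. This is an unspecified method, not a stated error, and a careful analyst might apply a correction anyway. That stands as a description, and every inflated figure here is conditional on the uncorrected sandwich and z test. It does not remove the problem, because nothing in the plan commits the analyst to a correction. A model-based variance with z also over-rejected in simulation (7.2–8.2% mixed, 8.0–9.4% constant).

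Other points have partial force:

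- **Range.** The range of 7.5–9.5% pools different cases. If clinics are mixed, as the Enrollment text may suggest, about 8% is the better single figure. Nor is 9.5% a ceiling: some equal-size runs and the unequal-size runs exceed it.
- **Sidedness.** Two-sided 5% is an assumption, and the SAP words its hypothesis directionally. A one-sided 5% test rejected 6.5–7.5% (mixed) or 7.6–8.3% (constant), so the inflation is smaller but remains.
- **Choice of correction.** Kauermann-Carroll + t and Mancl-DeRouen + z are both defensible. What matters is naming one in advance.
- **Power.** The 30% versus 45% example is illustrative. With no effect size, ICC or power target in the documents, it cannot show whether 400 patients are enough.
- **Decision-stage wording.** This is mainly a matter of wording and adds little to the severity.

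**Conclusion.** The concern holds and should be fixed. If the uncorrected sandwich with a z test is used on 20 clinics, the test of the main hypothesis has a type I error of about 7.5–9.5% at an assumed two-sided 5%. False positives are then about 1.5–1.6 times as frequent as intended if ethnicity varies within clinic (7.7/5 to 8.2/5), and 1.7–1.9 times if it is constant (8.7/5 to 9.5/5).

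The result depends little on the assumed ICC and screening rate, because it comes mainly from the number of clinics. It does depend on how ethnicity is distributed across clinics and on equal recruitment. Unequal clinic sizes, or further clinic-level covariates added for baseline imbalance, would push the error higher. The point estimate and the decision to use a clustered analysis are not affected.

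**What to change.** In the SAP paragraph on overall screening adherence, state:

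- GEE with logit link and exchangeable working correlation, clustered on the randomised clinic/physician;
- a bias-corrected sandwich variance (for example Kauermann-Carroll) with a t reference on 20 minus the number of clinic-level parameters: 18 df if only intercept and arm are clinic-level, 17 if ethnicity effectively is too;
- alpha and sidedness.

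The degrees of freedom should be fixed in advance, not judged from the data. If the ethnic mix of clinics is not known, 17 df is the cautious choice and widens intervals by only about 0.4% (2.110/2.101 = 1.004). Mancl-DeRouen with z is an acceptable alternative, and the better one if clinic sizes are expected to differ much. In the decision-stage paragraph, name the same corrected GEE model in place of the reference to a link function alone.

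**Cost.** One or two sentences and no extra patients. Relative to the uncorrected z interval, intervals become about 13% wider (ethnicity mixed), 15% (90/10 clinics) or 18% (constant), which is their valid width. Nominal power falls by about 6–12 points in the alternatives simulated. The power given up belonged to a test that rejected too often under the null.

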- (7) At 12 months after randomization, an endpoint medical record review will be performed on all study participants to assess colorectal cancer screening adherence. Self-reported colorectal cancer screening data will be collected by phone. Survey interviewer will ask participants if they had colorectal cancer screening in past 6 months.

Outcomes

Participants will complete a pen and pencil questionnaire at baseline. At 6-month follow-up, participants will participate in phone survey and their medical records will be reviewed. At 12-months after randomization, the medical records of all participants will be reviewed by research team staff. Phone follow-up will be conducted to collect self-reported data on colorectal cancer screening. Previously validated measures to assess belief, attitude, cohesion, self-resilience and knowledge about

colorectal cancer screening and colorectal cancer, health literacy, religion, social support, acculturation and colorectal cancer screening adherence will be used in baseline and 6-month surveys.

Primary Outcome Measure:

- **Colorectal Cancer Screening Adherence**
 - Description: measure to assess colorectal cancer adherence among participants
 - Time Frame: at 6-month and at 12-month
- **Overall colorectal cancer screening adherence by self-report and medical record review**
 - Description: measure overall colorectal cancer screening adherence by self-report and medical record review
 - Time Frame: at 6 months and at 12 months
- **Colorectal cancer screening decision stage for stool blood test and colonoscopy**
 - Description: measure colorectal cancer screening decision stage for stool blood test at baseline and 6 month
 - Time Frame: Baseline and 6-month
- **Change in colorectal cancer screening decision stage for stool blood test and colonoscopy**
 - Description: measure change in colorectal cancer screening decision stage for stool blood test and colonoscopy
 - Time Frame: 6 months
- **Colorectal cancer screening test-specific adherence for stool blood test and colonoscopy**
 - Description: measure the fraction of participants who undergo a stool blood test and colonoscopy
 - Time Frame: at 6 months and at 12 months

Ethical Considerations

This study was reviewed and approved by the University of Maryland, College Park Institutional Review Board. Prior to participation in the study, participants will provide informed consent.

Potential Risks and Discomforts

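### Baseline decision stage can enter the adherence model only through an undefined imbalance trigger, and the forward-change model is equally open

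*SAP*

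**What the plan says.** The SAP's paragraph on overall screening adherence specifies a GEE with logit link, participants nested within physicians, and gender, age and ethnicity as covariates. The reason given is not prognostic: "these three variables will be included to allow addition of interaction between study group and gender, age, or ethnicity in secondary analyses". Further covariates have one route in: "If, however, substantial baseline imbalances occur, the model will control for additional variables". The SAP does not define substantial, name candidate variables, or say who decides and when. The Protocol has no covariate plan.

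The SAP's paragraph on change in decision stage shows that stage is available at baseline: "We will elicit decision stage both at the baseline survey and at the 6-month survey". It has four ordered levels per test, and the plan will "compute an overall colorectal cancer screening decision stage as the higher of the two test-specific decision stages". Baseline stage is used there only to build the outcome: "Forward change (between baseline and 6-month) will encompass any movement from a lower to a higher decision stage". No change and backward movement both count as no. Covariates are again left open: "The model will adjust for participant baseline characteristics if necessary".

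The Protocol's Primary Outcome Measure list contains overall adherence ("measure overall colorectal cancer screening adherence by self-report and medical record review") and also change in decision stage, so both models serve outcomes labelled primary.

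**The concern.** A participant who has already decided to be screened is plausibly more likely to be screened than one who has decided against it. Leaving that variable out of the fixed model gives up precision. A trigger gives most of it up as well, because it adjusts only in trials where the arms happen to differ.

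Two analysts who read the trigger differently can also fit different models to the same data. With a logit link, those models estimate different odds ratios.

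For forward change, the link with baseline stage is not an assumption. Anyone who starts at the top stage cannot move up and is a no by definition. Taking the higher of two test-specific stages pushes people towards that ceiling.

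**Working it through.** **Inputs from the documents.** Protocol, Enrollment and Procedures (1): 20 clinics × 20 patients = 400; 10 × 20 = 200 per arm. Neither document gives alpha, power, screening rates, ICC, stage distribution or prognostic strength. There is therefore no figure of the plan's to reproduce, and everything below rests on assumed inputs.

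**1. How often would a trigger fire by chance?** The variance of one covariate's standardised difference is about (2/200)(1 + 19 × ICC).
- ICC 0: SD = √0.01 = 0.100. P(>0.1) = 32%, P(>0.2) = 5%, P(>0.25) = 1%.
- ICC 0.10: SD = √(0.01 × 2.9) = 0.170. P(>0.1) = 56%, P(>0.2) = 24%, P(>0.25) = 14%.

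If ten independent variables were screened (assumed), at least one would cross 0.1 in 98–100% of trials and 0.25 in 12–78%. Whether the model changes depends mainly on a cut-off that the SAP does not state.

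**2. Adherence, simulated power.** Assumptions: control rate 35.5%, intervention log-odds 0.8, clinic SD 0.35, stage latent ICC 0 to 0.10. Stage is scored 0–3 with shares 1/16, 3/16, 5/16, 7/16 (the higher of two independent uniform stages) or equal shares. The analysis was a logit GEE with independence working correlation, Kauermann-Carroll standard errors and t on 17 df, over 8,000 trials per cell; the Monte Carlo SE of a gain is about 0.3 points. Entries are trigger at 0.25 / trigger at 0.1 / stage always included, with the trigger acting on stage alone.

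| Odds ratio per stage | ICC 0 | ICC 0.05 | ICC 0.10 |
|---|---|---|---|
| 1.25 | .802/.801/.800 | .798/.801/.803 | .799/.801/.803 |
| 1.5 | .792/.794/.797 | .778/.784/.791 | .778/.786/.790 |
| 2.0 | .759/.772/.785 | .747/.766/.786 | .732/.755/.775 |
| 2.5 | .731/.746/.772 | .708/.735/.766 | .693/.737/.774 |
| 2.5, equal shares | .690/.714/.749 | .648/.695/.749 | .622/.685/.745 |

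By subtraction, always including stage gains −0.2 to 0.5 points at 1.25, 0.3 to 1.3 at 1.5, 1.3 to 4.3 at 2.0, and 2.6 to 8.1 at 2.5. With equal shares at 2.5 it gains 3.5 to 12.3 (largest: .745 − .622). With clinic SD 0.50 the gain at 2.5 is 2.0 to 6.1. A separate run of 1,500 trials per cell gave about 1–3 points at 1.5 and 4–12 at 2.5 against the 0.25 trigger.

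A second set-up (exchangeable correlation, intervention log-odds 0.65, 600 runs) agrees in direction. In its most favourable cell (log-odds 0.9 per stage), power was 51.7% without stage, 52.3% with a 0.25 trigger and 64.7% with stage always in.

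In the first set-up, reading substantial as 0.1 or as 0.25 selects a different model in 30–42% of trials. It changes the significance verdict in 1–7% (up to 9.5% with equal shares).

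**3. Forward change, simulated power.** The SAP names only a logit link with nesting; a GEE is assumed. Control movement is 35% below the top stage and impossible at it; intervention log-odds 0.8; 4,000 trials per cell.

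| Shares (at top) | ICC | Never | Trigger 0.25 | Trigger 0.1 | Always, linear |
|---|---|---|---|---|---|
| 1,3,5,7/16 (44%) | 0 | .533 | .534 | .545 | .568 |
| | 0.05 | .494 | .498 | .526 | .576 |
| | 0.10 | .448 | .460 | .503 | .559 |
| Equal (25%) | 0 | .668 | .669 | .679 | .693 |
| | 0.05 | .630 | .634 | .662 | .682 |
| | 0.10 | .618 | .629 | .657 | .690 |

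The linear term gains 1.4–5.6 points against a 0.1 trigger and 2.4–9.9 against 0.25. Allowing for smaller reruns, the ranges are about 1–6 and 2–12.

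**4. Linear term against a below-top comparison.** In a rerun of step 3 (2,000 trials per cell), restricting to participants below the top stage gave .626/.635/.616 at ICC 0/0.05/0.10, against .568/.582/.562 for the linear term. With equal shares it gave .737 against .704 (ICC 0) and .743 against .718 (ICC 0.10). A further run at ICC 0 gave .660 against .594, and .748 against .713 with equal shares. The extra gain is 2.5 to 6.6 points. The below-top odds ratio was 2.21–2.24 (generating value e^0.8 = 2.23); the linear-term odds ratio was 2.06–2.10.

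**5. Null rejection.** Adherence: 4.8–5.7% never adjusting, 4.7–5.4% always, 3.6–5.5% with triggers. Forward change: 4.3–5.3% in step 3 and 4.6–5.2% for both methods in step 4. Second adherence set-up: 2.2–4.5%.

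**The case against.** The current adherence model is a defensible one. It is pre-specified apart from an exception, and the SAP expects the arms to be comparable, so it is strained to read substantial as 0.1, a level that chance alone crosses in a third or more of trials. Between 0.2 and 0.25, adherence power differs by at most about 1.2 points. This stands: the figures for model and verdict disagreement compare two distant cut-offs and should be read as outer values.

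No document says how strongly stage predicts screening, and at weak prognosis the gain is within noise. The 44% at the top stage is also an assumption. Both points stand, which is why equal shares are shown, including where they reduce the gain.

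It can also be said that the stage ceiling belongs to the outcome definition and that covariate wording does not cure it. This stands too. A straight line on the logit misdescribes movement that is level below the top and zero at it. A separate top-stage category would have no events, so its coefficient could not be estimated.

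A reader might infer that the trigger biases the result or inflates type I error. The documents do not support that. Baseline stage precedes the intervention, the ceiling applies to both arms alike, and no inflation appeared. That last finding covers only a trigger on stage alone; the SAP speaks of additional variables, and a search over the many survey measures was not simulated.

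A reader might also take the SAP to restrict the model to three covariates in all cases. It does not: the trigger sentence itself widens it.

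**Conclusion.** The point holds as a matter of precision and pre-specification; no bias is shown. That the covariate sets are open in both models follows from the text and needs no assumption. The size of the adherence loss cannot be derived from the documents. It is near zero if stage is weakly prognostic, and the larger gains need an odds ratio of 2.0 to 2.5 per stage, combined with a high cut-off and clustering of stage by clinic.

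For forward change the case for fixed adjustment is firmer, because dependence on baseline stage is built into the outcome whenever anyone starts at the top. How many do so is unknown.

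One caution applies. Protocol Procedures lists clinic randomization as step 1 and consent with the baseline survey as step 2. If enrolment does follow allocation, the arms could differ through selective enrolment, and adjusting for stage would not fully remove that. The documents do not show that it happens.

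This should be changed. Confidence is medium.

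**What to change.** **Adherence paragraph.** Replace the imbalance sentence with a fixed main GEE: study group, gender, age, ethnicity and baseline overall decision stage, included whatever the observed balance, with a missing-stage indicator so that nobody is dropped. Keep imbalance-driven adjustment as a labelled sensitivity analysis with a named variable list and cut-off (for example, absolute standardised difference above 0.2); this also serves as a check on selective enrolment. Report a standardised risk difference with a cluster-robust interval beside the odds ratio, since the SAP's stated comparison is of proportions: "The two study groups will be compared in terms of the fraction of participants who undergo colorectal cancer screening".

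**Decision-stage paragraph.** Replace the open adjustment sentence with fixed adjustment for gender, age, ethnicity and baseline stage. Do not rely on a linear stage term alone: add a pre-specified comparison of forward change among participants below the top stage at baseline, and state that this changes the target population. The restriction uses a baseline variable, so it keeps the randomized contrast.

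**Cost.** SAP wording only, with no new data. The adherence model gains one participant-level term and an indicator. The small downside is that the adjusted odds ratio becomes conditional on stage (about 2.2 against 2.0 without it, at 2.5 per stage in the simulation), which is why the risk difference is reported with it.

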- (2) All 400 participants will be invited to primary care physician's clinic or community organization, where the participant will provide informed consent and HIPAA authorization form and complete a baseline survey (see sample). Participants' height, weight and waist/hip circumference, blood pressure, blood glucose and cholesterol levels will be measured by trained research staff.
- (3) Those randomized to the advanced control group will receive informational booklet regarding colorectal cancer and colorectal cancer screening, colonoscopy instructions, stool blood test kit and a result of body measurements as a free service. They will receive a reminder by mail after 45 days of random assignment.
- (4) Those randomized to the culturally adapted decision support navigation intervention group will receive everything the advanced control receives, and will receive a phone call from a patient navigator. The patient navigator will verify the participant's preferred colorectal cancer screening test. During this encounter, the patient navigator will also use a theory-based online Decision Counseling Program© to identify barriers to and facilitators of preferred test performance, determine the likelihood of test performance, and develop a personal screening plan. The counseling call will take about 45 minutes. The patient navigator will print out this screening plan and share it with the participant and primary care physician's office. After 45 days of random assignment, those in the culturally adapted decision support navigation intervention group will receive a reminder by mail.
- (5) Six months after randomization, trained and blinded bilingual survey interviewers will contact each participant by telephone and administer a 6-month Survey. This will take about 20 minutes. Six-month medical record review will be also completed by the survey interviewer.
- (6) The patient navigator will create a colorectal cancer screening status report for participants in the culturally adapted decision support navigation intervention, and share it with the primary care physician and office manager. The report will indicate whether the participant adhered to the screening, and if the participant needs diagnostic follow-up for an abnormal stool blood test result.

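### The decision-stage scale has no level for completed screening, so a participant who screened by 6 months can be scored as not having moved forward, which may attenuate the between-arm contrast

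*SAP*

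**What the plan says.** The SAP paragraph on change in decision stage sets four rules.

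- **Levels.** "We will elicit colorectal cancer screening decision stage separately for stool blood test and colonoscopy (decided against, not considering, undecided, decided to do". The top level is an intention.
- **Overall stage.** The plan will "compute an overall colorectal cancer screening decision stage as the higher of the two test-specific decision stages".
- **Timing.** "We will elicit decision stage both at the baseline survey and at the 6-month survey".
- **Scoring.** "Forward change (between baseline and 6-month) will encompass any movement from a lower to a higher decision stage". The outcome is binary: "yes vs. no (no change or backward movement between baseline and 6 months".

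The hypothesis is that intervention participants "will have a greater likelihood of forward movement in screening decision stage than participants in the advanced group". The SAP's adherence paragraph also expects more screening in that arm.

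The Protocol makes screening before month 6 likely. Its inclusion criteria admit only people who are not up to date. Under Procedures (3) the control arm receives, among other things, a "stool blood test kit and a result of body measurements as a free service", with a mailed reminder at 45 days. Under Procedures (4) the intervention arm receives the same, plus a navigator call and a personal screening plan. Screening is also recorded at the same time point: the Outcomes section says that measures of several constructs and of "colorectal cancer screening adherence will be used in baseline and 6-month surveys", and medical records are reviewed at 6 months. Neither document links that information to the decision stage.

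**The concern.** At 6 months the scale asks people who may already have had the test whether they intend to have it. There are two routes by which a screener is scored 'no'.

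1. **Ceiling.** A participant at 'decided to do' at baseline who then screens has nowhere higher to go. The score is 'no change' by construction.
2. **No matching answer.** A participant who began lower, say 'undecided', and completed the stool test may give a low intention answer because the test is done. If neither the stool-test nor the colonoscopy answer exceeds the baseline overall stage, the score is 'no'.

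Both routes affect only people who screened, and the trial expects more of them in the intervention arm. Part of the intervention's success could then be counted as failure in this outcome. Change in decision stage is part of specific aim 2, is listed under the Protocol's primary outcome measures, and is one of only two between-group analyses in the SAP.

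**Working it through.** The documents give no screening rate, stage distribution or target effect for this outcome, so there is no planned figure to reproduce. The check is algebra on the scoring rule, followed by an illustration with assumed inputs.

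**Inputs (all assumed)**

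- s: share screened by 6 months; 0.60 intervention (sT), 0.40 control (sC)
- b: share at the top level at baseline; 0.25, equal in both arms and unrelated to screening
- f: share of non-screeners below the top at baseline who move forward; 0.40 in both arms
- q: share of screeners below the top at baseline who are scored forward; varied from 1 to 0, equal in both arms

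**Formulas**

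- With a 'done' level: P = s + (1 - s)(1 - b)f
- Four levels as written: P = s(1 - b)q + (1 - s)(1 - b)f

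**With a 'done' level**

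- Intervention: 0.60 + 0.40 × 0.75 × 0.40 = 0.72
- Control: 0.40 + 0.60 × 0.75 × 0.40 = 0.58
- Risk difference +0.14, odds ratio 1.86

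**Four levels as written**

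| q | Intervention | Control | Risk difference | Odds ratio |
|---|---|---|---|---|
| 1 | 0.45 + 0.12 = 0.57 | 0.30 + 0.18 = 0.48 | +0.09 | 1.44 |
| 0.5 | 0.225 + 0.12 = 0.345 | 0.15 + 0.18 = 0.33 | +0.015 | 1.07 |
| 0.4 | 0.18 + 0.12 = 0.30 | 0.12 + 0.18 = 0.30 | 0 | 1.00 |
| 0 | 0 + 0.12 = 0.12 | 0 + 0.18 = 0.18 | -0.06 | 0.62 |

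**Separating the two routes.** The risk difference lost is (sT - sC)[1 - (1 - b)q], which splits into:

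- ceiling: (sT - sC)b = 0.20 × 0.25 = 0.05, whatever q is
- no matching answer: (sT - sC)(1 - b)(1 - q) = 0.15(1 - q), which is 0 at q = 1, 0.075 at q = 0.5 and 0.15 at q = 0

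The drop from +0.14 to +0.09 is therefore all ceiling, and anything beyond it comes from the second route. Nothing is lost if b = 0 and q = 1.

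**When the sign changes.** With equal f, the four-level risk difference is (1 - b)(sT - sC)(q - f) = 0.15(q - 0.40). It is negative only when q is below f, that is, when screeners are scored forward less often than non-screeners.

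**If the intervention also moves non-screeners** (f = 0.50 versus 0.40), the risk difference with a 'done' level is 0.75 - 0.58 = +0.17. On four levels it is +0.12 at q = 1, +0.045 at q = 0.5, +0.008 at q = 0.25 and -0.03 at q = 0. Reversal then needs a lower q.

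**Odds-ratio scale.** The SAP models the logit. Over a grid of 19,152 assumed scenarios (intervention screens more, f at least as high in the intervention arm, b = 0 with q = 1 left out), the risk difference always shrank and it reversed in 21%. In 1.5% the odds ratio was larger on four levels than with 'done'. These are shares of a grid, not probabilities.

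**The case against.** **The instrument is not shown.** The 6-month questionnaire may have an 'already done' answer or a skip pattern. This stands as a limit on any claim about size. It does not close the gap, because the SAP lists four levels and gives no rank to a fifth.

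**The higher-of-two rule protects some screeners.** A participant who was undecided overall and has done the stool test still counts as forward if either test is answered 'decided to do'. This stands, and it is why q need not be small. It gives no help to someone who began at the top.

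**The two outcomes are meant to differ.** Decision stage measures intention and adherence measures behaviour; counting every screener as forward merges them in part. This also stands. In the illustration with equal f, the whole +0.14 arises from the screening difference. It is a reason to show both versions, not to leave screeners unstaged.

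A reader might draw three stronger conclusions that the documents do not support:

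- That the effect will reverse. That needs q below f, and nothing in the documents indicates it.
- That screeners are generally scored as failures. One who began below the top and answers 'decided to do' is scored forward.
- That screeners who leave the items blank are dropped. The SAP states no missing-data rule for this outcome, so their handling is unknown.

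**Conclusion.** The gap is real: the scoring rule has no place for completed screening, and nothing elsewhere in the documents supplies one. A 'no' is certain only for a screener who began at 'decided to do'; for other screeners it depends on their 6-month answers. Given more screening in the intervention arm, the likely consequence is attenuation of the between-arm contrast, with reversal a conditional risk.

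The size cannot be known from the documents. The illustrated fall from +0.14 to between +0.09 and -0.06 rests on assumed screening rates, baseline ceiling and movement among non-screeners, with b and q equal across arms. Confidence is high that the rule is missing and moderate that it would bias the result materially. The 12-month adherence analysis is unaffected.

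**What to change.** Before arm-level results are seen, add to the SAP: *A participant with a stool blood test or colonoscopy between the baseline survey and the 6-month survey, by 6-month survey or record review, is assigned a top stage, 'done', at 6 months, whatever the answers to the intention items. Forward change is assessed on this five-level scale.*

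Two reporting additions go with it:

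- the 6-month stage distribution by arm with 'done' shown separately, so that intention among the unscreened stays visible
- the four-level, intention-only forward-change result as a sensitivity analysis

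The cost is one sentence, a recode of data already planned for collection at 6 months, and one extra model. The recoded outcome partly overlaps with adherence, so the two results should not be presented as independent evidence. The sentence also gives a stage to a screener who leaves the intention items blank; the SAP should still say how blank items from non-screeners are handled.
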